2.9 Physical Activity Monitoring

Wearable devices that can monitor steps taken, stairs climbed, energy expenditure, heart rate, and sleep metrics are now marketed as fitness trackers. Data from these user-friendly and inexpensive devices may provide important information to clinicians caring for cancer patients^{78,79}. In a series of trials we have performed at Montefiore/Einstein, we have discovered that a simple measure – daily step count – can provide valuable prognostic information regarding both short-term hospitalization risk⁸⁰⁻⁸² and long-term clinical outcomes⁸³.

Baseline activity level (based on step count average and age) can predict clinical outcomes for patients treated with chemoradiotherapy for locally advanced NSCLC (left, middle)⁸³ or patients receiving palliative systemic therapy for advanced solid tumors (right, preliminary data from an ongoing trial)

Subjects on this trial may opt to wear a commercial fitness tracker (provided by the study team) as part of this study. We will assess baseline activity level as a prognostic factor for study subjects and also compare rates of activity change for subjects who receive study therapy versus standard care, with the expectation that study therapy will preserve physical function compared to standard therapy, such as cytotoxic chemotherapy.

3.0 PATIENT ELIGIBILITY

3.1 Inclusion Criteria

- Histologically proven NSCLC, not classically deemed to be amenable to curative therapy based on disease extent at the time of diagnosis or disease progression after the initial diagnosis

[figure not shown]
- Age \geq 18 years
- Prior treatment with at least two lines of systemic therapy for advanced NSCLC, including one line of platinum-based combination chemotherapy
 - Treatment with concurrent chemotherapy and immunotherapy can count as two lines of therapy for the purposes of study eligibility.
- Radiological assessments, including CT within 21 days prior to study entry and PET/CT within 42 days prior to study entry, demonstrating measurable disease that includes at least one pulmonary or extrapulmonary lesion \geq 1 cm in greatest dimension that would be amenable to SBRT and at least one measurable lesion that would be outside of the SBRT treatment fields
- ECOG performance status 0-2
- Both men and women enrolled in this trial must agree to use adequate birth control measures during the trial and for at least 90 days after last receipt of study therapy. Patients and/or partners who are surgically sterile or postmenopausal are exempt from this requirement.
- The following laboratory results, within 21 days prior to study registration:
 - Hemoglobin \geq 9.0 g/dL
 - Absolute neutrophil count \geq 1.5 \times 10⁹/L
 - Platelet count \geq 100 \times 10⁹/L
 - Serum creatinine \leq 1.5 \times ULN OR creatinine clearance (by Cockcroft-Gault formula) $>$ 60 mL/min
 - AST and ALT \leq 2.5 \times ULN
 - Total bilirubin \leq 2.0 \times ULN (except patients with Gilbert's syndrome, who must have a total bilirubin \leq 3.0 mg/dL)
 - Negative SARS-CoV-2 (COVID-19) PCR test
 - COVID-19 testing may be repeated periodically based on institutional policies and must be repeated for any subject with unexplained signs (e.g., imaging findings, fever) or symptoms (e.g., anosmia) concerning for COVID-19 infection or with recent known exposure to COVID-19.

3.2 Exclusion Criteria

- Prior therapy with any anti-CD40 antibody or FLT3 ligand
- Less than 21 days between planned study treatment start and the last receipt of chemotherapy, targeted cancer therapy, immunotherapy, radiotherapy (excluding palliative radiotherapy), or major surgery.
- Untreated central nervous system metastases. Patients with a history of brain metastases must have had no CNS-directed therapy within the past 60 days and radiological assessment within 30 days of study entry demonstrating a lack of progressive CNS disease. Patients without a history of brain metastases and without symptoms suggestive of brain metastasis do not require staging imaging of the brain prior to study enrollment.
- Known mutation/amplification in FLT3
- Ongoing use of high dose oral corticosteroids (\geq 2 mg of dexamethasone daily or equivalent) or inhaled corticosteroids. Intranasal and/or intraarticular corticosteroid use is permitted.

- History of non-infectious pneumonitis or any ongoing pneumonitis
- History of allogeneic organ transplant or active autoimmune disease
- Other active malignancy for which systemic therapy (excluding hormonal therapy for breast or prostate cancer) is indicated.
- History of myocardial infarction, cerebral vascular accident, thrombosis, or pulmonary embolus within 12 months prior to study registration.
- Uncontrolled intercurrent illness including, but not limited to, symptomatic congestive heart failure, unstable angina pectoris, uncontrolled cardiac arrhythmia, or psychiatric illness/social situation that would limit compliance with study requirements as judged by the treating physicians
- Active infection requiring systemic therapy, known HIV infection, or positive test for hepatitis B surface antigen or hepatitis C (antibody screen and if positive confirmed by RNA analysis). If positive results are not indicative of a true active or chronic infection, the patient can be enrolled after discussion with, and agreement by, the Principal Investigator.
- Receipt of a live vaccine within 30 days prior to the first dose of study drug. Examples of live vaccines include, but are not limited to, the following: measles, mumps, rubella, varicella/zoster (chicken pox), yellow fever, rabies, Bacillus Calmette–Guérin (BCG), and typhoid vaccine. Seasonal influenza vaccines for injection are generally killed virus vaccines and are allowed; however, intranasal influenza vaccines (e.g., FluMist®) are live attenuated vaccines and are not allowed.
- *Subjects who are not ambulatory or ambulate using a walker are not eligible for the objective activity monitoring component of this study.*

4.0 STUDY DESIGN

¹EGFR/ALK positive v. EGFR/ALK negative or unknown

²Limited Disease (suitable for comprehensive SBRT) v. Extensive Disease

^aIncluding comprehensive SBRT for limited disease

- Safety assessment for Phase I will take place after 6 subjects are randomized to Arm 1 and followed for 8 weeks after treatment initiation
- If ≤ 1 subject out of 6 on Arm 1 experiences a DLT, the study will proceed to Phase II
- The total sample size (Phase I + Phase II) will be 46 subjects

4.1 General Design

This is a randomized, open-label phase I/II study. Subjects will be randomized in a 1:1 ratio to receive FLT3 ligand, anti-CD40 antibody, and SBRT (Arm 1) versus standard care (Arm 2). Subjects on either study arm with limited disease will receive SBRT to all evident sites of active disease. Subjects on Arm 1 with extensive disease will initially receive SBRT to a single site of disease but may receive additional “cycles” of FLT3 ligand, anti-CD40 antibody, and SBRT at later time points. Subjects on Arm 2 with extensive disease are expected to receive some form of standard systemic therapy (e.g., docetaxel). Subjects on Arm 2 with limited disease may also receive standard systemic therapy following completion of SBRT to all sites of evident disease, at the discretion of the treating physicians. All subjects will be followed closely for treatment-related toxicities. Whole-body PET/CT and CT imaging will be performed prior to study entry, and restaging CT will be performed every 8 weeks thereafter.

In the phase I component of this study, subjects will be randomized between study arms until 6 subjects have been randomized to Arm 1. Study accrual will then be halted until 8 weeks after the last study subject begins treatment.

If the pre-specified safety criteria are achieved in the Phase I portion of this study, the study will proceed to phase II. The total sample size (Phase I and Phase II) will be 46 subjects. All 46 subjects will be included in efficacy analyses.

If the pre-specified safety criteria are not achieved in the Phase I portion of this study, the investigators and Celldex will review safety data from this trial as well as other trials using CDX-301 and CDX-1140 and determine if the experimental treatment regimen should be altered (e.g., by reducing the CDX-1140 dose). The study protocol would be amended accordingly, and Phase I component with the new treatment regimen would be added.

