8.2 Phase I Primary Endpoint – Dose-Limiting Toxicity

A stopping rule for safety will be implemented as follows: After 6 subjects are randomized to Arm 1 (which will take place after approximately 12 total subjects are enrolled), accrual will be temporarily suspended for DLT monitoring. 8 weeks after the 6th subject on Arm 1 starts treatment, the study will proceed to Phase II if no more than one out of six subjects on Arm 1 has experienced a DLT (defined in Section 7.2).

If the pre-specified safety criteria are not achieved in the Phase I portion of this study, the investigators and Celldex will review safety data from this trial as well as other trials using CDX-301 and CDX-1140 and determine if the experimental treatment

regimen should be altered (e.g., by reducing the CDX-1140 dose). The study protocol would be amended accordingly, and Phase I component with the new treatment regimen would be added.

At the conclusion of the trial, study therapy will be considered safe and worthy of further study if no more than 4 out of 23 subjects on Arm 1 experience a DLT. The target Grade 3 toxicity rate is no more than 12.5%, and a toxicity rate greater than 35% is considered clinically unacceptable. This design has the following operating characteristics: The probability of accepting the treatment for further study if the true toxicity rate is unacceptably high (>35%) is at most 5%. In contrast, there is at least an 85% probability of accepting the treatment for further study if the true toxicity rate is less than 12.5%.

The proportion of patients on Arm 1 who develop a DLT will be computed, along with Clopper-Pearson 95% exact confidence intervals. Frequencies of specific treatment-related adverse events (including delayed adverse events) and event grades will be characterized using counts and percentages.

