10.4 Data Safety and Monitoring Board

The Albert Einstein College of Medicine/Albert Einstein Cancer Center Data Safety Monitoring Committee (DSMC) has the responsibility for ensuring data and

safety monitoring along with the PI who is ultimately responsible for the ongoing monitoring and safety of clinical protocols. The primary functions of the AECC DSMC are as follows:

1. To review and ensure protocol compliance with dose escalation in phase I trials
2. To review/assure protocol compliance for all trials that have two-stage phase II designs,
3. Reviewing all internal and external serious adverse reports, investigator alerts, action letters, and other safety reports for trials being performed at AECC-affiliated institutions and;

To implement and to determine the adequacy of DSM plans of all approved protocols.

The DSMC is an independent committee and meets on a bimonthly basis. During its bimonthly meeting, the DSMC will review serious (grade 3 or higher) adverse events from this study. In the event that the DSMC decides that a protocol revision is warranted, the committee will immediately notify the principal investigator of this study. The DSMC has the authority to close trials to patient accrual should the risk to patients be excessive or outweigh the potential benefits of the study. All study suspensions and closures will be forwarded to the IRB/CCI and study sponsor from the DSMC. The DSMC will review all safety data from Phase I before the study proceeds to Phase II.

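### Neither safety criterion suspends randomisation to Arm 1 at the point where it can no longer be met

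*Combined protocol and SAP*

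**What the plan says.** Section 4.1 sets the Phase I accrual rule: "subjects will be randomized between study arms until 6 subjects have been randomized to Arm 1. Study accrual will then be halted". Section 8.2 repeats it: "After 6 subjects are randomized to Arm 1 (which will take place after approximately 12 total subjects are enrolled), accrual will be temporarily suspended". The reading comes "8 weeks after the 6th subject on Arm 1 starts treatment", and "the study will proceed to Phase II if no more than one out of six subjects on Arm 1 has experienced a DLT". If the gate fails, both sections send the data to the investigators and the drug supplier for review, with a possible amendment and a new Phase I component.

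Section 8.2 then gives a second criterion. "At the conclusion of the trial, study therapy will be considered safe and worthy of further study" on the condition "if no more than 4 out of 23 subjects on Arm 1 experience a DLT". No look at this count is planned between the Phase I gate and the end of the trial.

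Other safeguards are in Sections 10.4 and 11.2. On the DSMC, Section 10.4 says: "During its bimonthly meeting, the DSMC will review serious (grade 3 or higher) adverse events from this study". The committee can close accrual if risk is excessive and reviews the Phase I safety data before Phase II opens. The principal investigator carries ultimate responsibility for ongoing monitoring. Section 11.2 requires SAEs to be reported within 24 hours to the principal investigator, to the trial office for forwarding to the IRB and DSMC, and to the drug supplier.

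**The concern.** A DLT count can only rise. Once two of the first six Arm 1 subjects have had a DLT, the 1-of-6 gate has failed, whatever happens to the rest. Once five Arm 1 subjects have had one, the 4-of-23 criterion has failed. The plan attaches a halt to neither event, so a site that follows the text exactly can go on randomising to the experimental arm after the outcome of the safety criterion is fixed.

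What is at stake is avoidable exposure. Section 5.2.6 reports four cases of severe treatment-related pneumonitis with CDX-1140 monotherapy; two patients were intubated, and two later died of documented or presumed infection.

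**Working it through.** **Inputs from the plan.** Gate at most 1 of 6 and final criterion at most 4 of 23 (8.2); acceptable and unacceptable toxicity rates 12.5% and 35% (8.2); DLT window 8 weeks (7.2); 1:1 allocation and 46 subjects, so 23 on Arm 1 (4.1); accrual over 24 months (8.3).

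**The plan's own figures.** For the 23-subject criterion alone, P(accept) = P(X ≤ 4), X ~ Bin(23, p). This gives 5.5% at p = 0.35 (stated: at most 5%) and 84.8% at p = 0.125 (stated: at least 85%). Both are close to the stated values, which therefore describe the end-of-trial criterion without the gate.

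**Can DLTs be known in time?** Arm 1 accrues 23/24 = 0.96 subjects a month, so six take about 6/0.96 = 6.3 months. Eight weeks is 8/4.345 = 1.84 months, or 1.84 × 0.96 = 1.8 Arm 1 subjects. A DLT can therefore be known before later subjects enter.

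**Exact probabilities (independent DLTs, constant rate).**
- Gate passed: (1−p)^6 + 6p(1−p)^5. At 0.35: 0.0754 + 0.2437 = 0.319, so the gate fails in 68.1% of trials. At 0.125: 0.8335, so it fails in 16.7%.
- Fifth DLT reached, given a pass: 0.866 at 35% and 0.099 at 12.5%.
- Both, over all trials: 0.319 × 0.866 = 27.6% at 35%; 0.8335 × 0.0991 = 8.3% at 12.5%.
- Accepted under both rules: 0.3191 − 0.2763 = 4.3% at 35%; 0.8335 − 0.0826 = 75.1% at 12.5%.

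**Arm 1 subjects randomised after the criterion has failed.** The plan gives no DLT onset pattern, so two assumptions are shown.

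(a) Simulation, 60,000 trials per rate: exponential Arm 1 arrivals at 23/24 a month, DLT onset uniform over days 8 to 56, each DLT known at onset, and a 56-day pause after subject 6.

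(b) Enrolment order with a fixed lag: each DLT becomes known only after two more Arm 1 subjects have entered (8 weeks of accrual, 1.8 rounded up).

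| At a true rate of 35% | (a) | (b) |
|---|---|---|
| Mean further Arm 1 subjects after the 2nd DLT, given gate failure | 1.3 | 0.6 |
| Mean further Arm 1 subjects after the 5th DLT, given pass and 5th DLT | 5.3 | 4.4 |
| Phase II mean over all trials | 0.276 × 5.3 = 1.5 | 0.276 × 4.4 = 1.2 |

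Under (a), among trials that fail the gate at 35%, 63% randomise at least one more Arm 1 subject after the second DLT is known, 42% randomise two or more, and 37% randomise none. The median after a fifth DLT is 5.

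**Effect of a pause.** It acts only when the count has already passed 1 of 6 or 4 of 23. If resuming accrual does not undo that failure, the acceptance probabilities stay at 4.3% and 75.1%.

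**The case against.** The strongest reply is that the plan is not without protection. SAEs travel within 24 hours to the principal investigator and onward to the DSMC, the committee can close accrual, and it sees all Phase I safety data before Phase II. A reader might infer that the two-monthly meeting is the only backstop; Section 11.2 does not support that. What remains is narrower. These routes rest on judgement and carry no DLT number, and a DLT need not be an SAE: Section 7.2 counts, for example, ALT or AST above 8 × ULN whatever its duration, and a treatment delay of more than two weeks for toxicity that is not improving.

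A second reply is that 4 of 23 is a go/no-go judgement for further study, not a stopping boundary. That is correct. A reader might infer that the fifth DLT declares the regimen unacceptable, but the plan reserves that term for a true rate above 35%. Five of 23 is 21.7% (exact 95% interval 7.5% to 43.7%), and five or more occur with probability 15% even at a true rate of 12.5%. This is a reason to suspend and review rather than to terminate.

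Third, later subjects are not without value. They cannot change the pass/fail result, but they add to the DLT proportion and its interval, to the adverse event frequencies, and to the PFS analysis of all 46 subjects. This also favours a suspension that the DSMC can lift.

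**Conclusion.** The gap is real. No pre-specified rule suspends randomisation when the second Phase I DLT or the fifth DLT has made the criterion unattainable. At 35%, the Phase I cost is modest: 0.6 to 1.3 Arm 1 subjects per failed gate. The Phase II cost is larger where it occurs, 4.4 to 5.3 Arm 1 subjects, but only about 28% of trials pass the gate and then reach a fifth DLT, so it averages 1.2 to 1.5 per trial. The conditional figure of about 87% reaching a fifth DLT after a pass should not be read as applying to all trials, because at 35% only 32% pass.

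These sizes rest on independent DLTs at a constant rate, the planned accrual, and the two assumed onset patterns. That the criteria are not tied to a halt rests on none of them.

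This is a recommended, low-cost improvement, strongest for Phase II. Sections 4.1, 8.2 and 10.4 are consistent with one another on this point, so it should not be presented as a contradiction or an analysis error.

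**What to change.** Add to Sections 4.1 and 8.2, in substance: randomisation is suspended as soon as a second DLT is recorded among the first 6 Arm 1 subjects on a given regimen, in which case the Phase I criterion is not met and the existing review and amendment pathway applies. It is also suspended as soon as a fifth DLT is recorded among Arm 1 subjects on that same regimen. The DSMC is notified at once, and accrual resumes only after its review. DLTs are counted separately for any amended regimen. Resuming accrual does not reverse a failed 1-of-6 or 4-of-23 criterion.

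The last two sentences are needed. Without them, DLTs from an abandoned regimen could be pooled with those of its replacement, and a restart could be taken to reopen a settled verdict.

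The cost is this short text and a running DLT count; the trial is open-label, so no unblinding is involved. Accrual may be delayed, or PFS left with fewer subjects. At the acceptable rate of 12.5%, about 8% of trials would reach the fifth-DLT pause. The 16.7% that fail the gate at that rate are already stopped for review under the existing text, so there the change only brings the halt forward.

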4.2 Study Calendars

4.2.1 Pre-Registration and Pre-treatment Assessments

	Timing
CBC, BMP, LFTs	Within 21 days prior to study entry
Amylase, Lipase	Pre-treatment
Negative SARS-CoV-2 PCR	Within 21 days prior to study entry
PET/CT	Within 42 days prior to study entry
CT C/A/P	Within 21 days prior to study entry
QoL Assessments	Pre-treatment
Correlative Study Blood Draw	Pre-treatment ¹
CDX-301 ADA and CDX-1140 PK	Pretreatment (Arm 1 only) ¹

1. Must be obtained at least 21 days after last receipt of chemotherapy, targeted cancer therapy, immunotherapy, radiotherapy (excluding palliative radiotherapy), or major surgery.

4.2.2 Arm 1 (experimental study arm)

ARM 1	Week 1	Week 2	Week 4	Week 6	Weeks 9 ¹ , 17 ² , 25 ² , 33 ² , 41 ² , 49 ²
History and Physical Examination	X	X ⁵ X ⁶	X	X ⁵ X ⁶	X
CBC, BMP, LFTs, Amylase, Lipase	X	X ⁵ X ⁶	X	X ⁵ X ⁶	X
Activity Data Download ³	X	X	X	X	X
QoL Assessments		X	X	X	X
Correlative Study Blood Draw		X ⁷		X ⁷	X
CDX-301 ADA and CDX-1140 PK		X ⁷ X ⁸ X ⁶		X ⁷ X ⁶	
CT C/A/P					X
Stereotactic Radiotherapy (SBRT) ⁴	XXX				
FLT3 Ligand (CDX-301)	XXXXX				
CD40 Agonist Antibody (CDX-1140)		X		X	

1. +/- 1 week

2. +/- 2 weeks

3. For subjects who opt to participate in this part of the study

4. SBRT should be delivered in 1, 3, or 5 fractions per target and may continue beyond Week 1 when treating multiple sites.

5. On the day of CDX-1140 infusion

6. One day after CDX-1140 infusion

7. Immediately before CDX-1140 infusion

8. 2 hours after CDX-1140 infusion

Cycles of SBRT(to an untreated lesion)+CDX-301+CDX-1140 may be repeated.

- At least 8 weeks must separate the start of each treatment cycle.
- CDX-1140 may be omitted from retreatment cycles for subjects with prior DLT or intolerable toxicity attributed to CDX-1140.
- The schedule of assessments will reset when a new cycle is initiated.

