4.2.3 Arm 2 (control arm)

ARM 2	Week 1	Week 2	Week 4	Week 6	Weeks 9 ¹ , 17 ² , 25 ² , 33 ² , 41 ² , 49 ²
History and Physical Examination	X	X	X	X	X
CBC, BMP, LFTs, Amylase, Lipase	X	X	X	X	X
Activity Data Download ³	X	X	X	X	X
QoL Assessments		X	X	X	X
Correlative Study Blood Draw		X		X	X
CT C/A/P					X
Stereotactic Radiotherapy (SBRT) ⁴	XXX				

1. +/- 1 week

2. +/- 2 weeks

3. For subjects who opt to participate in this part of the study

4. SBRT is only required for subjects with limited disease burden.

SBRT should be delivered in 1, 3, or 5 fractions per target and may continue beyond Week 1 when treating multiple sites.

Standard systemic therapy may be administered at any time for subjects with extensive disease burden and any time after completion of all planned SBRT for subjects with limited disease.

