5.2.2 Treatment Schedule

CDX-301 and CDX-1140 will only be administered to subjects on Arm 1. Subjects on Arm 2 will not “crossover” if disease progression is observed. The Study Calendar (Section 4.2) describes the timing of study drug administrations.

Some subjects on Arm 1 may receive more than one “cycle” of CDX-301, CDX-1140, and SBRT (targeting a lesion not previously treated with SBRT). The decision to administer treatment cycles beyond cycle 1 must be agreed upon by the treating physicians, the principal investigators, and the study subject. Additional treatment cycles will not be offered to subjects who develop disease progression within four months of receiving a previous cycle of study therapy or to subjects who have no evidence of active disease. Subjects who previously experienced DLT or intolerable toxicity related to CDX-1140 may be treated with CDX-301 and SBRT and without CDX-1140 in subsequent treatment cycles.

For subjects who receive more than one cycle of study therapy, the schedule of events will reset at the beginning of each cycle. At least 8 weeks must separate the start of each treatment cycle.

CDX-301

Five injections of CDX-301 should be administered daily during Week 1 (Monday-Friday) of a treatment cycle. If that is not possible due to department closure for a national holiday, inclement weather, or another reason that is not treatment-related toxicity, CDX-301 treatment may extend to Week 2 (though not beyond 10 days after the first CDX-301 dose).

CDX-1140

The first CDX-1140 will take place 4 days (+/- 1 day) after the last dose of CDX-301. As CDX-301 will typically be given from Monday-Friday, CDX-1140 will usually be given on a Tuesday. The second dose of CDX-1140 will be given 4 weeks (+/- 3 days) after the first CDX-1140 dose. CDX-1140 will not be administered on a Friday, as a clinic visit the day after each CDX-1140 dose is required.

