5.2.4 Potential Toxicities and Toxicity Management

Potential toxicity and guidance for the management of toxicity is summarized below. However, the CDX-1140 and CDX-301 Investigator Brochures (IB) are the Single Reference Safety Documents that provide complete and relevant information about the known safety profile of CDX-1140 and CDX-301.

CDX-301

CDX-301 was generally well-tolerated in all prior studies, including our prior study of CDX-301 and SBRT for advanced NSCLC, which utilized the same CDX-301 dose/schedule as the present trial. The most frequently observed toxicities related to CDX-301 have been asymptomatic lymphadenopathy and mild injection site reactions.

Injection site reactions have been infrequent and mild with CDX-301. No injection site reactions were observed in our recent trial combining CDX-301 and SBRT (29 subjects, 180 injections). Generally mild to moderate injection site reactions were reported in studies using AMG949. Pre-medication with diphenhydramine has been reported to be effective in the prevention of pruritic and erythemic reactions⁹³ and may be considered for subjects who experience local reactions after treatment with CDX-301. Injection site reactions may also be treated with analgesics (i.e., Tylenol). If there is injection site pain, a numbing cream such as Emla cream can be used prior to administration of CDX-301. Patients will be monitored for 30 minutes following each CDX-301 injection.

Leukocytosis, especially monocytosis, is expected during administration of CDX-301. Hematological parameters, including WBC and differential, should be monitored in subjects receiving CDX-301. CDX-301 should not be administered if marked leukocytosis, e.g. WBCs greater than 50,000 cells/mm³, is observed.

CDX-1140

The CDX1140-01 study was the first clinical trial with CDX-1140, and therefore there is limited clinical experience to define expected toxicities. Management of drug-related adverse events and serious adverse events should be in accordance with the institution's standard of care and guidelines for managing immune related toxicities⁹⁴.

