7.3 Radiographic Assessments

Pre-registration imaging will be obtained prior to study entry and will consist of a whole-body PET/CT (within 42 days) and a diagnostic CT of the chest, abdomen, pelvis (within 21 days). The surveillance imaging schedule is detailed in the Study Calendars (Section 4.2) and includes CT of the chest, abdomen, and pelvis every 8 weeks for one year. CT imaging of the pelvis may be omitted for patients with no history of metastatic lesions in the anatomical area. Intravenous and oral contrast will be used, unless a contraindication to contrast administration exists. Additional imaging studies (e.g., FDG-PET, MRI) may be added at any time to assess disease that is not well-visualized on CT and/or if there is concern for disease progression. The surveillance imaging schedule beyond year 1 will be left to the discretion of the treating physicians but should follow current guidelines⁷⁵.

Subjects with a history of brain metastases will undergo surveillance for the development of new/progressive brain metastases. Imaging timing and details will be left to the discretion of the treating physicians but will generally follow current guidelines¹⁰⁷ and most often include high-resolution MRI of the brain with i.v. contrast every 2-3 months. Prompt MRI of the brain is recommended for any study subject who develops symptoms suggestive of new/worsening brain metastasis.

Tumor response and progression-free survival (PFS) will be assessed using iRECIST criteria (Appendix) and secondarily using RECIST criteria.

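### A new Arm 1 cycle resets the assessment calendar with no exemption for CT, so PFS scan dates can depend on arm; the expected effect is small, can run either way, and is cheap to remove

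*Combined protocol and SAP*

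**What the plan says.** The Arm 1 calendar (Section 4.2.2) lists CT C/A/P at Weeks 9, 17, 25, 33, 41 and 49, with a window of 1 week either side for the first and 2 weeks for the others. Below it stands: "The schedule of assessments will reset when a new cycle is initiated". Section 5.2.2 repeats the rule for subjects given more than one cycle: "the schedule of events will reset at the beginning of each cycle". Neither sentence sets tumour imaging apart.

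Only Arm 1 can have such a reset. Section 5.2.2 states that "CDX-301 and CDX-1140 will only be administered to subjects on Arm 1" and rules out crossover, and the Arm 2 calendar (Section 4.2.3) has the same CT weeks and no reset. Cycle starts must be at least 8 weeks apart, but nothing ties a new cycle to a scan date. Subjects who are progression-free and have active disease are not barred from retreatment.

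Three other places point to a fixed grid:
- Section 4.1: "restaging CT will be performed every 8 weeks thereafter".
- Section 7.3 gives CT at 8-week intervals during the first year, without distinguishing the arms, and refers to the Study Calendars for detail. It adds: "The surveillance imaging schedule beyond year 1 will be left to the discretion of the treating physicians".
- Appendix C (iRECIST) says that assessment dates belong on a calendar and are not to move when treatment is delayed.

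**The concern.** Section 4.3 scores PFS by iRECIST from registration, and Appendix C dates a confirmed progression at the scan that first met the criteria. The scan grid is thus part of how the endpoint is measured. If the grid moves in one arm because of a treatment decision made in an open-label trial, recorded PFS times can differ between arms for a reason unrelated to disease. A site must also choose between Section 4.1 and Section 4.2.2 when it books the next CT, and sites or physicians may choose differently. In a 46-subject trial this is avoidable variation in the primary endpoint.

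**Working it through.** **The plan's own figure.** Section 8.3 gives medians of 5 and 10 months, 24 months of accrual, 12 months of further follow-up, no loss, 46 subjects and two-sided alpha 0.20. With exponential PFS, P(event) = 1 − [exp(−12λ) − exp(−36λ)]/(24λ), which is 0.945 on Arm 2 and 0.788 on Arm 1. Expected events are 23 × (0.945 + 0.788) = 39.9. Power is Φ(√39.86 × ln 2 / 2 − 1.2816) = 0.818, which agrees with the stated 81%.

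**Scan interval.** A cycle started d weeks after a CT puts the next CT 8+d weeks after that CT: 10, 12 and 14 weeks for d = 2, 4 and 6. At d = 0 nothing changes, and small shifts fall within the visit windows. Example: CT at Week 25 ± 2 and a new cycle in Week 28. The next CT is due at Week 28 + 8 = 36 ± 1 on Arm 1, against Week 33 ± 2 on Arm 2. The gap is 8 to 14 weeks against 4 to 12. Scheduled CT then runs to Week 28 + 48 = 76, against Week 49.

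**Added detection delay per retreated subject.** Let q(x) = exp(−ln 2 · x / median), and take a subject progression-free at the last CT. Expected time to detection is 8/(1 − q(8)) on the fixed grid and (8+d) + q(8+d) · 8/(1 − q(8)) after a reset. The difference is 8 + d − 8(1 − q(8+d))/(1 − q(8)).

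| d (weeks) | median 5 months (21.74 weeks) | median 10 months |
|---|---|---|
| 2 | 0.30 weeks | 0.15 weeks |
| 4 | 0.70 | 0.37 |
| 6 | 1.21 | 0.64 |

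**Share retreated (assumption).** This trial states none. Section 5.2.4 reports 29 subjects and 180 injections in the prior trial, and Section 2.4.2 gives 5 injections per course. That is 180/5 = 36 courses, 7 more than 29, so at most 7/29 = 24% retreated if courses were complete. At 24%, the 5-month delays average 0.07, 0.17 and 0.29 weeks over Arm 1, or 0.5 to 2.0 days.

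**Effect on the log-rank test** (simulation, 23 per arm, one reset per retreated subject, scans 8-weekly throughout):

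| Scenario | Benefit-side error, 5 v 5 months | Two-sided error | Power, 10 v 5 months |
|---|---|---|---|
| Visit windows, no reset | 10.4% | 21.1% | 80.3% |
| 24%, d = 2, 4 or 6 after the first or second scan | 10.7–11.1% | 21.2–21.3% | 80.2–80.9% |
| Exact grid, no reset | 10.0% | 20.8% | 81.2% |
| Exact grid, 24% of those progression-free, fixed gaps of 2, 4 or 7 weeks | 8.9–10.2% | 20.9–21.1% | 79.4–81.4% |

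A second set with windows, 24% of those progression-free retreated and gaps uniform on 0 to 8 weeks moved benefit-side error from 10.5% to 10.8–11.1%. With every progression-free Arm 1 subject retreated at Week 9, it was 11.6%.

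**Direction.** Measure time from the last CT before the reset. True progression in weeks 0 to 8 is recorded d weeks later than on the fixed grid. Progression between weeks 8 and 8+d is recorded at 8+d instead of 16, which is 8 − d weeks earlier. With d = 6, progression in weeks 8 to 14 is recorded 2 weeks earlier than on Arm 2. The average is a delay, but the test also responds to which arm's scans come first. That is why the exact-grid results fall on both sides of 10.0%.

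**After Week 49.** At the planning medians, 0.465 × 23 = 10.7 Arm 1 and 0.216 × 23 = 5.0 Arm 2 subjects are still progression-free at 48 weeks. Extra scheduled CT for retreated Arm 1 subjects would tend to find their progression earlier. This works against Arm 1 and is not in the simulations.

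**The case against.** Sections 4.1 and 7.3 and Appendix C all point to a fixed grid, so a reader could take the reset to cover only treatment-linked assessments. That reading is reasonable, but the text does not establish it. CT is a row of the schedule that resets, Section 7.3 refers back to the calendars, and the Appendix C sentence concerns delayed treatment, not new cycles. What stands is that the plan is inconsistent, not that it clearly intends an arm-specific scan rule.

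The exposure may also be overstated, and most of this stands. Section 4.1 mentions further cycles only for Arm 1 subjects with extensive disease. Retreatment needs an untreated lesion and active disease, which a subject given comprehensive SBRT would often lack. Courses given after progression cannot alter PFS, yet the 24% counts them all. Retreatment would plausibly follow a recent scan, making d small. Against this, the prior trial allowed new cycles after 4 months and this one allows them from 8 weeks. Unscheduled imaging for suspected progression (Section 7.3) would shorten some long gaps.

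A reader might infer that the reset biases PFS in favour of Arm 1 enough to threaten the result. The documents do not support that: no retreatment rate is given, plausible rates move the test by about a point or less, and the sign depends on the gap. A reader might also infer that the confirmatory scan after unconfirmed progression is lost. It is not, because the 4-to-8-week rule in Appendix C applies whatever the cycle start.

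**Conclusion.** The point holds at low severity. As written, the reset gives Arm 1 subjects retreated before progression a different CT grid from Arm 2. It does not fit the 8-week interval in Sections 4.1 and 7.3 or the fixed-calendar principle in Appendix C. The expected size is about 0.3 to 1.2 weeks of added detection delay per retreated subject at a 5-month median, and about 1 percentage point or less of benefit-side error at 24% retreated. The direction is not fixed. These figures assume exponential PFS, progression found only at scans, one reset per subject and a retreatment share borrowed from the prior trial. The reason to act is that a scan rule depending on arm is easy to remove, not that it is expected to change the conclusion. The sample size and the stated 81% power are unaffected.

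**What to change.** Reconcile Sections 4.1, 4.2.2, 5.2.2 and 7.3 and the Appendix C calendar sentence with one statement. Visits, laboratory tests, PK/ADA, QoL and correlative draws reset with a new cycle. Tumour CT for PFS stays on the original 8-week calendar (Weeks 9 to 49) in both arms until progression, whatever the cycle start. Unscheduled imaging remains allowed as in Section 7.3, and confirmatory scans as in Appendix C.

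The cost is a short clarification and an occasional separate scan visit for a retreated subject. Treatment, alpha and sample size do not change. Scheduled CT need not be extended past Week 49: once CT no longer resets, it ends at Week 49 in both arms, and Section 7.3 deliberately leaves later imaging to the treating physicians. Extending it would add about 62 scheduled CTs at the planning medians (46 on Arm 1 and 16 on Arm 2), which this point does not justify.
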